Harms will be assessed by monitoring changes in weight, eGFR, CBC, clinic BP, and ABPM. For more definitive assessments, including hospitalizations, serious adverse events will be properly completed and sent to the VAMC DMC as requested. Safety of continued participation will be assessed at each study visit. The stop-points will be treatment-emergent severe adverse events that precludes further exposure to the drug, such as an allergic drug reaction, initiation of renal replacement therapy, or death. If the study drug is stopped, the subject will be continued to be studied so as to not violate the intention-to-treat principle.

Participants

Inclusion Criteria

- Stage 3 or 4 CKD defined as eGFR <60mL/min/1.73m² for ≥3 months or persistent albuminuria for ≥3 months; (i) urine albumin to creatinine ratio of more than 30 mg/g; (ii) urine protein to creatinine ratio of more than 150 mg/g; or (iii) at least 1+ dipstick positive proteinuria. ⁸⁸
- 24h ABPM <140/90 mmHg at baseline in the presence or absence of antihypertensive treatment.
- Hgb between 8 and 10 g/dL.
- No treatment with ESA within the previous 3 months.
- Adults, age 18 and older.

Exclusion Criteria

- Need for packed RBC transfusion in the previous 2 months.
- Myocardial infarction, stroke, or hospitalization for heart failure in the past 2 months.
- In the assessment of the investigator, have hematologic, inflammatory, infectious, or other conditions that might interfere with the erythropoietic response.

Retention of Participants

For half of the participants, only 7 visits are needed. For the others, at least 11 visits over 24 weeks of the trial are needed. We will offer \$20 per visit for participation in the trial to offset travel and time costs.

METHODS

Method of Randomization

Participants will be randomized in a 1:1 ratio to either early or delayed treatment (“waitlisted group”) with EPO according to UACR strata. A random permuted block design will be used to avoid imbalance in assignment to the treatment groups over time. A randomization sequence will be generated by the statistician and individually concealed in sequentially numbered opaque envelopes. After confirming eligibility with the principal investigator, the study pharmacist will dispense EPO according to the randomization sequence.

Measurement of clinic BP

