Clinic BP measurements will be obtained by a trained observer in triplicate in both arms after applying an appropriately sized cuff using a digital oscillometric sphygmomanometer (Model HEM-907, Omron Healthcare) following the recommendation of the European Society of Hypertension ⁸⁹. The arm and the forearm will be supported at the level of the heart (mid-sternum) and oscillometric BP will be measured after 5 min of seated rest without an observer in the room. Measurements averaged over three readings at 1 min intervals will be used to define clinic visit BP. The left arm will be used for all measurements, unless between arm reading exceed 5 mmHg systolic. If so, the arm with the higher BP will be designated the “BP arm” and will be used for clinic BP measurements. If a subject has dialysis access (AV fistula or AV graft), we will use their non-access arm for all BP measurements.

Measure of 24-hour ambulatory BP

Ambulatory BP monitoring will be performed in all participants at baseline prior to randomization and at the end of the treatment period as indicated in **Figure 2**. Appropriately sized cuffs will be used with bladder sizes that encircle 80–100% of arm circumference and widths that are at least 40% of arm circumference. We will measure ABP every 20 minutes from 06:00 – 22:00 and every 30 minutes from 22:00 – 06:00 based upon a prior protocol using the use the Spacelabs 90207 monitor ¹⁷. Participants will be asked to record their wake and sleep times into diaries; the latter are used to calculate diurnal ambulatory BP. At least 16 recordings will be required to call 24h BP adequate (excluding readings taken for monitor validation during ambulatory dispensing). All ambulatory BP measurements will be taken on a subject’s non-dominant arm. If a subject has dialysis access, all BP measurements will be completed on the non-access arm.

Measurement of endothelial dysfunction

We will instruct the participants to fast for eight hours, refrain from caffeine, alcohol and tobacco and avoid exercise for 8 hours prior to testing. Endothelial function testing will be performed using flow-mediated dilatation (FMD) in a quiet, temperature-controlled room with dimmed lights after the participant has been resting for at least 15 minutes in the recumbent position using international recommendations ⁹⁰.

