The number of subjects who experience hypokalemia, hypercalcemia, gout, hospitalization for diabetes mellitus, transient elevations in serum creatinine concentration, and symptomatic orthostatic hypotension will be counted for each group and compared using a Poisson regression model using terms for treatment and treatment x stratum. The statistical significance of the treatment term will be used to indicate differences between CTD and placebo. If the interaction term is significant then the event rates will be reported for each stratum. The mean change from baseline in serum potassium, calcium, estimated GFR, uric acid, HgbA1C, PTH intact, and orthostatic BP will be calculated using mixed models as noted above.

Alternative study design considerations and clarifications

Choice of non-dialysis patients. Dialysis patients are challenging to study because it is more difficult to determine hypertension due to confounding by dry weight. Angioaccess makes it difficult to perform FMD. Furthermore, the number of dialysis patients—in contrast to CKD patients not on dialysis—is limited.

Timetable/Milestones

We expect to recruit and randomize a total of 160 participants in the first 3.5 years and complete the study in 4 years. This will require approximately 1 participant to be randomized per week. See table below.

Table 1: Timeline for randomization in the trial (t = 4y, n = 160)

	Year 1				Year 2				Year 3				Year 4			
Quarter	1	2	3	4	1	2	3	4	1	2	3	4	1	2	3	4
Patients	x	16	16	16	16	12	12	12	12	10	10	10	10	8	x	x

Feasibility

A feasibility assessment was performed using data from the Veterans Administration's Corporate Data Warehouse (CDW), a national repository of data compiled from the electronic medical record (EMR) system used by the Veterans Health Administration (VHA). These data include current and historical values from multiple domains such as patient medications, vitals, labs, procedures, and diagnoses, and are available from October 1st, 1999 forward. Of note, these data are updated on a daily basis and are neither filtered nor validated prior to entry into the CDW. We will use these values to screen potentially eligible participants. It is only possible to uniquely identify potential participants by accessing their EMRs using real social security numbers.

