To determine the number of prospective subjects meeting eligibility criteria for the study, a query of all patients seen at the Roudebush VA Medical Center (VAMC) in Indianapolis was performed by the VA Informatics and Computing Infrastructure (VINCI) staff. The query sought to identify adults (at least 18 years of age) seen at the Roudebush VAMC in the past 4 weeks with CKD 3-4 (eGFR 15-60 mg/dL/1.73m²), anemia (Hgb 8-10 g/dL), and controlled clinic BP (<140/90) without receipt of an erythropoiesis-stimulating agent (ESA) within the past 12 weeks. The initial query returned 140 eligible prospective subjects. The following month, the same query returned 28 new eligible prospective subjects.

It is estimated that approximately 25% of eligible prospective subjects will consent to the study visits and, of these, 67% will randomize to the treatment (e.g., early vs. delayed start of EPO). Since we require ambulatory BP monitoring as an inclusion to participate in the trial, we expect approximately 33% of the patients to fail this criterion. After a robust recruitment in the early quarters, we expect the number of eligible participants to drop and therefore we expect fewer patients in the later quarters. Extrapolating from the feasibility data, we project that recruitment will begin in the second quarter of the first year and end by the third quarter of the fourth year from receipt of the grant, which gives us the following table.

Data and safety monitoring plan (DSMP)

We have prepared a DSMP to specify the process by which the PI will review the progress of the trial and the safety of its participants. Periodic assessments of these data will be done in addition to mandatory reporting requirements of the IRB

REFERENCE LIST

2. van de BP, Tielemans C, Vanherweghem JL, Degaute JP. Effect of recombinant human erythropoietin therapy on ambulatory blood pressure and heart rate in chronic haemodialysis patients. *Nephrol Dial Transplant* 1992;7(1):45-49.
(<http://www.ncbi.nlm.nih.gov/pubmed/1316580>).
3. Anonymous. Effect of recombinant human erythropoietin therapy on blood pressure in hemodialysis patients. Canadian Erythropoietin Study Group. *Am J Nephrol* 1991;11(1):23-26.

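### The inclusion criterion is labelled stage 3 or 4 CKD, but its definition is wider at both ends of the eGFR range and does not explicitly exclude dialysis

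*Combined protocol and SAP*

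**What the plan says.** The Inclusion Criteria in the Participants section ask for "Stage 3 or 4 CKD defined as eGFR <60mL/min/1.73m² for ≥3 months or persistent albuminuria for ≥3 months". The albuminuria route is then spelled out by thresholds, "i) urine albumin to creatinine ratio of more than 30 mg/g; (ii) urine protein to creatinine ratio of more than 150 mg/g", with a positive dipstick as a third option. None of the three thresholds is tied to an eGFR value.

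There are three Exclusion Criteria. They cover recent transfusion ("Need for packed RBC transfusion in the previous 2 months"), recent cardiovascular events, and conditions that could blunt the erythropoietic response. Dialysis, renal replacement therapy and a minimum eGFR do not appear.

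Other sections describe a narrower population:

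- Feasibility counts the eligible pool with a query for "CKD 3-4 (eGFR 15-60 mg/dL/1.73m²), anemia (Hgb 8-10 g/dL), and controlled clinic BP (<140/90". It has no albuminuria route.
- Alternative study design considerations and clarifications has an entry that begins "Choice of non-dialysis patients. Dialysis patients are challenging to study". It gives dry weight and vascular access as the reasons.
- Safety Assessments and Variables lists starting renal replacement therapy among the stop points.
- Study Intervention says participants are found through eGFR and hemoglobin.

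One instruction points the other way. Measurement of clinic BP says: "If a subject has dialysis access (AV fistula or AV graft), we will use their non-access arm for all BP measurements". The ambulatory BP section gives a similar instruction.

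**The concern.** The phrase that introduces the definition makes it the operative rule. A coordinator who applies it literally would accept patients the rest of the protocol does not have in mind.

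- **Upper end.** The background section on the importance of CKD concludes that underlying CKD is needed for EPO-induced hypertension. It relies on rats with subtotal nephrectomy. That evidence does not establish a BP response in people with albuminuria and preserved eGFR. If their response is weaker, they dilute the treatment effect.
- **Lower end.** Patients with eGFR below 15 fall outside stages 3 and 4 and outside the feasibility count.
- **Dialysis.** The protocol explains its own avoidance of this group: "Dialysis patients are challenging to study because it is more difficult to determine hypertension due to confounding by dry weight". It adds that access makes FMD hard to perform. These problems touch the primary endpoint and the main mechanistic endpoint, yet no eligibility rule states the exclusion.

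At stake are the match between enrolled and described populations, the consistency of eligibility decisions, and possibly some power in a trial planned at 80%.

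**Working it through.** **1. Written rule against feasibility query.** The rule is eGFR <60 or albuminuria. The query is eGFR from 15 to 60.

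| eGFR | Albuminuria | Meets written CKD rule | Inside query |
|---|---|---|---|
| 8 or 14 | no or yes | yes | no |
| 15, 30 or 59 | no or yes | yes | yes |
| 60 | no | no | yes |
| 60 | yes | yes | yes |
| 75 or 95 | no | no | no |
| 75 or 95 | yes | yes | no |

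The rule is wider than the query below 15, and above 60 when albuminuria is present. The mismatch at exactly 60 without albuminuria is trivial.

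**2. The plan's sample size.** Inputs from the Sample Size section: SD of change 10.3 mmHg, difference 5 mmHg, two-tailed, 80% power, 85% completing. Alpha is not stated; I assume 0.05.

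- Normal approximation: n = 2 × (1.960 + 0.842)² × 10.3² / 5² = 66.6, so 67 per group.
- t-based: 67.6, so 68 per group, as stated.
- Randomized: 68 / 0.85 = 80 per group, 160 in total, as stated.

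The calculation reproduces, and the eligibility wording does not alter it.

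**3. Sensitivity to dilution (illustration only).** Suppose a share s of patients in each arm is out of range and has no BP response. The mean effect is then 5 × (1 − s). The SD stays at 10.3 with 68 completers per arm; power is from the two-sided t-test.

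| Share s | Mean effect (mmHg) | Power |
|---|---|---|
| 0% | 5.00 | 80.2% |
| 1% | 4.95 | 79.5% |
| 2% | 4.90 | 78.6% |
| 5% | 4.75 | 76.1% |
| 10% | 4.50 | 71.5% |
| 20% | 4.00 | 61.3% |

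If out-of-range patients had half the response, a 10% share would give 5 × (1 − 0.10 × 0.5) = 4.75 mmHg, and so 76.1%. The documents supply neither the share nor the response, so this table is not a forecast. It fits the upper end better than the lower: patients with eGFR below 15 do have reduced kidney function, and nothing in the background suggests they would not respond.

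**The case against.** The strongest reply is that the intent is clear and practice follows it. Participants are identified by eGFR and hemoglobin. A blood count and eGFR panel are drawn at the consent visit, while UACR is first scheduled at baseline. Hemoglobin must be 8 to 10 g/dL, the investigator may exclude conditions that interfere with erythropoiesis, and eligibility is confirmed with the principal investigator before drug is dispensed. All this stands, and it probably keeps the number of out-of-range patients low. It does not remove the conflict, because screening practice is not an eligibility rule, and label and definition cannot both govern.

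Two stronger readings are tempting and are not supported:

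- **A reader might infer that the protocol plans to enrol dialysis patients.** It does not. They are only not explicitly excluded. The stage label, the design rationale and the renal-replacement stop point all show the opposite intent. The access-arm instruction does not prove enrolment, since access can be placed before dialysis starts.
- **A reader might infer that the background rules out a BP response when eGFR is preserved.** It says underlying CKD is necessary, not reduced eGFR, and albuminuric patients meet the protocol's own CKD definition. The endothelin section even reports a BP rise with EPO in un-nephrectomized mice that overexpress endothelin-1. A zero response is therefore an assumption, and no single power figure from it should be quoted as the expected loss.

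It can also be said that relabelling the population as CKD in general would resolve the conflict. It would, but it would depart from the stage 3-4 population on which the feasibility count rests.

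**Conclusion.** The point holds as a contradiction in the eligibility wording. Admission of albuminuric patients with eGFR of 60 or more is explicit in the text. Admission of patients with eGFR below 15 follows from the missing lower limit. For dialysis the defect is an omission: the intent to exclude is evident but not written as a rule.

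The practical size is unknown and probably modest. Under the assumptions in the working, power would range from about 79.5% at a 1% share to about 61% at 20%. The sample size calculation itself is sound. The change is worth making because the rule as written enrols outside the described population and correcting it costs almost nothing.

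**What to change.** Reconcile the Inclusion Criteria, the BP measurement sections, the rationale for non-dialysis patients and the Feasibility section so that the operative rule matches the stated population:

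- State the eGFR range explicitly as 15 to <60 mL/min/1.73m² for at least 3 months, in line with the feasibility query.
- State that patients on dialysis are excluded. If the access-arm instruction stays, say that it concerns access in patients not on dialysis.
- Do not let albuminuria alone qualify a patient as stage 3 or 4. Keep UACR as the stratification factor. The analysis model already has a stratum for no albuminuria, so albuminuria is not needed for entry.

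The cost is a wording change. The feasibility counts (140, then 28 new the following month) already used eGFR 15-60, so little or no loss is expected against the projection. One caution remains: the query as described states no 3-month persistence requirement, so those counts may slightly overstate the pool that meets the criterion. The documents do not allow that to be quantified.

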	UACR (x3)		x	x	x	x	DS	DS	DS
	Biomarkers		x	x		DS	DS		
Group	Immediate Start		x	x	x				
	Delayed Start		x	x	x	x	x	x	x

*CBC, Renal Panel, Ferritin, TSAT

** V1 if consent: CBC & eGFR panel

DS = Delayed Start ONLY

This is a two-arm, open-label, single-center, randomized controlled trial to understand the mechanisms of EIH. Participants will be randomized based on stratum of baseline level of urine albumin/urine creatinine ratios (UACR) measured on three consecutive days. The primary analysis will compare the 80 participants in the early start group to the 80 in the delayed start (DS) or waitlisted group over the first 12 weeks. All procedures will be performed as listed in the table based on study visit. Confirmatory analysis will compare the first 12 weeks to the next 12 weeks in the DS group. Accordingly, the study procedures labeled DS will be performed only in the delayed start randomized participants.

Study Intervention

Participants with CKD and anemia who meet the inclusion and exclusion criteria will be randomized to either the immediate or delayed start group. There are at least 7 study related visits in the early start group, and 11 in the waitlist group. Two consecutive days are needed to perform 24h ambulatory BP monitoring, which will be done twice in the immediate start group and 3 times in the delayed start group. Patients will receive oral iron (ferrous sulfate, 324 mg orally twice daily) if serum ferritin concentration is <100 ng/mL or transferrin saturation is <20%. If clinic BP exceeds either 179 mmHg systolic or 109 mmHg diastolic or if clinic BP raises by >20/10 mmHg compared to baseline, antihypertensive medication dose will be increased or a new antihypertensive will be added.

Participants will be identified in the renal clinic or the electronic medical record system based on estimated GFR and Hgb. At baseline, all participants will have 24-h urine Na measured to assess dietary Na intake.

Treatment Adherence

We recognize the limitations of syringe count, but we will assess treatment compliance with the study drug by performing a syringe count at each of the study visits.

Protocol for the management of anemia

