Longitudinal resting images will be acquired before inflation. Blood flow estimated by the pulsed Doppler velocity signal using the outer envelope technique to calculate the velocity time integral will be obtained from a mid-artery sample volume at baseline and upon immediate cuff release to assess hyperemic velocity. Peak hyperemic velocity will be determined from the first complete velocity envelope after cuff release. Higher values of hyperemic velocity represent better microvascular dilatation ⁹³. Longitudinal images of the artery in B mode will be continuously recorded for 3 min after cuff deflation. Images will be recorded digitally using an R-wave gated digitizing interface external to the machine (MIA- LLC, Coralville, IA).

A few minutes after deflation, another image will be acquired to reflect a reestablished baseline. The above procedure is repeated to acquire the images in

deviation of 0.93% and between-subject standard deviation of 1.77%. Thus, the test-retest coefficient of variation was 7.2% in our laboratory.

Biomarker measurements

We may use specimen collected as part of this study for analysis of DNA which may include whole genome sequencing. Plasma endothelin-1 will be measured using validated ELISA kits (R&D systems, Inc., Minneapolis, MN). 24h urinary nitrite and nitrate and total nitrates will be measured using the Greiss reaction using kits from R&D systems, Inc. Renin and aldosterone will be measured using a commercial laboratory (LabCorp, Burlington, NC). Plasma ADMA will be measured using LCMS in our biochemistry core lab. The usual labs such as blood counts, chemistries, urine albumin and Na will be measured in the hospital laboratory. Renin + aldosterone lab testing will require the participants to be resting in seated position for at least 15 minutes prior to blood draw.

STATISTICAL METHODS

Outcome Variables

The outcome variables are as follows:

1. Change from baseline to 12 weeks in diastolic BP in EPO treated patients compared to delayed start controls. In the waitlisted group, we will measure the change from 12 weeks to 24 weeks compared to the change from 0 to 12 weeks.

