- model 1: The outcome variable will be 24h ambulatory diastolic BP. The predictors will be indicator variables for group (early or late start), time (baseline and 12 weeks), stratum (UACR: none, high, very high) and all interactions. The random component of the mixed model will include subject and time. Unstructured covariance will be used with estimation of marginal means by maximum likelihood. We expect the interaction between group by time to be significant. The random coefficient analysis does not require baseline systolic BP as a covariate. If the 3-way interaction term (group x time x stratum) is significant, then results will be reported within each stratum. Confirmatory analyses will utilize change from baseline in clinic diastolic BP.
- model 2: The outcome variable will be 24h ambulatory diastolic BP. The predictors will be indicator variables for period within the delayed start group (early or late), time (baseline and 12 weeks from start of period), stratum (UACR: none, high, very high) and

all their interactions. The random component of the mixed model will include subject and time. We expect the interaction between period by time to be significant. If the 3-way interaction term is significant, then results will be reported within each stratum.

Accounting for missing data

Ambulatory BP recording, the gold-standard to assess BP, is carried out only twice during the trial in the parallel group analysis, but clinic BP measurements occur every 4 weeks. Patients who drop out but have some post-baseline measurements of clinic BP will be included in the analyses, thus minimizing loss to follow up. We will impute ambulatory BP as follows: we will use the complete data to build a model that relates the follow-up mean 24-hour ambulatory diastolic BP from the baseline 24-hour ambulatory diastolic BP and the clinic measures using repeated measures Mixed Model regression - then use the expected value from the model for the missing value - and use PROC MI (which generates maybe 5 replicate values to insert variability into the imputation) so that there is a price to pay for imputing.

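### The entry-screen ABPM is also the week-0 outcome value, so regression to the mean biases the delayed-start period contrast (model 2) toward no EPO effect; model 1 is unaffected

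*Combined protocol and SAP*

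**What the plan says.** - **Entry.** The Inclusion Criteria require "24h ABPM <140/90 mmHg at baseline in the presence or absence of antihypertensive treatment".
- **Recordings.** The section on measuring 24-hour ambulatory BP says "Ambulatory BP monitoring will be performed in all participants at baseline prior to randomization". Study Intervention says of the monitoring: "which will be done twice in the immediate start group and 3 times in the delayed start group". Figure 2 places the delayed-start recordings at baseline, week 12 and week 24. No separate qualifying recording is described, so the screening value is the week-0 value.
- **Contrast.** Outcome Variables, item 1: "In the waitlisted group, we will measure the change from 12 weeks to 24 weeks compared to the change from 0 to 12 weeks". Model 2 under Primary Analysis fits this as a period-by-time interaction and adds: "We expect the interaction between period by time to be significant". The trial design section calls the comparison confirmatory.
- **Failure rate.** Feasibility, on the ABPM requirement: "we expect approximately 33% of the patients to fail this criterion".

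No section mentions regression to the mean or any adjustment for selection on the baseline value.

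**The concern.** A cap applied to a noisy reading keeps some patients whose value was low by chance. Their next reading rises on average with no treatment. In the delayed-start group this rise falls entirely in the untreated control period, because no cap applies at week 12. The control-period change is therefore too large, and subtracting it from the EPO-period change understates the EPO effect.

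Model 2 sits under Primary Analysis with a stated expectation of significance. A small or null result could be read as evidence against model 1 when part of it comes from the entry rule.

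**Working it through.** **Inputs from the documents.** SD of change 10.3 mmHg diastolic and 16.7 mmHg systolic; mean 24h diastolic BP 68.3 mmHg; target 5 mmHg; 68 completers per group; about 33% failing the ABPM criterion (Sample Size; Feasibility).

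**Assumptions not in the documents.** Total SDs of diastolic/systolic 24h BP of 10/15, 12/18 or 14/20; correlation ρ between systolic and diastolic visit errors of 0.5-0.85, with 0 as an extreme; true-level correlation 0.5; normality; independent visit errors; 4-week variability carried over to 12 weeks; two-sided alpha 0.05 (alpha is not stated).

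**1. The plan's own figure.** n = 2(1.96 + 0.84)² × 10.3²/5² gives 67 per group. The t-based version gives 67.6, so 68, and 68/0.85 = 80. The stated sample size reproduces.

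**2. Form of the bias.** The contrast is (Y24 − Y12) − (Y12 − Y0) = Y24 − 2·Y12 + Y0. Only the error in Y0 is selected. Its mean among those admitted is negative, so the contrast is shifted down by the full regression to the mean.

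**3. Diastolic limit alone.** The within-subject variance is 10.3²/2 = 53.0. With a = (90 − 68.3)/SD, the bias is (53.0/SD) × φ(a)/Φ(a). At SD 10, a = 2.17 and the bias is 0.20 mmHg; across SDs of 9-14 it is 0.13-0.48 mmHg. The diastolic limit matters little.

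**4. Through the systolic limit.** The error covariance is ρ × (10.3 × 16.7)/2 = 86.0ρ. If a fraction f fails on systolic BP, the diastolic bias is about (86.0ρ/SD of systolic BP) × φ(z)/(1 − f), with Φ(z) = 1 − f. At f = 0.33 the last factor is 0.54. With ρ = 0.7 and systolic SD 18 this gives (60.2/18) × 0.54 = 1.8 mmHg.

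**5. Both limits, by simulation**, with mean systolic BP set to give each failure rate:

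| Failing on BP | ρ | Bias in diastolic contrast (mmHg) |
|---|---|---|
| 33% | 0.5-0.85 | 1.3-2.7 |
| 10-20% | 0.5-0.85 | 0.6-1.7 |
| 10-33% | 0 | 0.1-0.5 |

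At 12/18, ρ = 0.7 and 33% failing, the simulation gives 1.86, in line with step 4. The matching untreated systolic rise at 33% failing and ρ = 0.5-0.85 is about 3.7-5.1 mmHg.

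**6. Power of the contrast.** Its SD is √3 × 10.3 = 17.8 mmHg, so with 68 completers its SE is 17.84/√68 = 2.16. Power is Φ(d/2.16 − 1.96):
- no bias, d = 5: 64%
- bias 1.3, d = 3.7: 40%
- bias 2.7, d = 2.3: 19%

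**7. Gap between the two models.** Model 1 minus model 2 reduces to the immediate-start week 0-12 change minus the delayed-start week 12-24 change. Its SE is 10.3 × √(2/68) = 1.77. A bias of 1.3-2.7 mmHg is 0.7-1.5 SE, so the two estimates would differ significantly in about 11-33% of trials.

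**The case against.** **The size rests on unstated inputs.** This stands. Mean systolic BP, the total SDs and the error correlation are not given, and mean diastolic BP is far below 90. A reader might infer that the plan's own figures fix a loss of a quarter to a half of the 5 mmHg target; they do not. At ρ of 0-0.3 with 33% failing, the bias is about 0.2-1.0 mmHg.

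**The 33% is a rough recruitment figure.** This also stands. Feasibility expects 67% of consenting patients to be randomized and assigns the whole remainder to the ABPM criterion, leaving nothing for other failures. The query behind it had already restricted to controlled clinic BP.

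**BP management could offset the drift.** Antihypertensive treatment is increased after a specified clinic BP rise, in the untreated period too. The documents do not allow the net effect to be sized.

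**The source cohort showed almost no drift** (mean difference 0.14 mmHg). The plan does not say that cohort was selected on a baseline ABPM limit, so this does not show that a capped sample is stable.

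**A mixed model handles it.** It does not, because screen failures are absent from the data being fitted.

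**It is only confirmatory.** This is true, and it limits the consequence. A reader might infer that the primary result is biased as well. It is not: both arms pass the same screen before randomization, so the artefact cancels in model 1. A reader might also expect an open conflict between the two models; step 7 shows that a significant one would be uncommon.

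**Conclusion.** The point holds for the within-group contrast only. The mechanism and direction follow from the documents: one recording serves as both screen and week 0, the second period has no matching selection, and the contrast is pulled toward no EPO effect.

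The size is uncertain, from a few tenths of a mmHg to about 2.7 mmHg. The upper part of that range needs a failure rate on BP near 33% and well-correlated systolic and diastolic errors. The practical consequence is lost power and an easily misread null result in a contrast that has only about 64% power without any bias. Confidence is high on direction and moderate at best on magnitude.

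**What to change.** In the SAP:

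- **(a)** Report the delayed-start week 12-24 change, with its confidence interval, on its own beside the period contrast.
- **(b)** State in advance that the week 0-12 change contains regression to the mean from the entry criterion. The raw period-by-time contrast is therefore biased toward zero, and a smaller or non-significant result is not evidence against model 1.
- **(c)** As a sensitivity analysis only, fit baseline systolic and diastolic BP jointly with the follow-up ABPMs. Include the baseline ABPMs of consented patients who failed the criterion, where these are retained, with their follow-up treated as missing.

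**Cost.** (a) and (b) need only SAP wording and make the claim for the confirmatory analysis more modest. (c) needs a somewhat larger model and screen-failure recordings, which the documents do not say are kept for analysis. It relies on normality, extrapolates above 140/90 and refers to the screened population. In simulation, standardising to all screened patients left 0.01-0.03 mmHg of drift under normality, but over-corrected by about 0.7-0.8 mmHg when true systolic BP was right-skewed. That is why it should not replace the main contrast.
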